### 5.1 ReCharge CHW intervention description

The ReCharge intervention is package of services designed to address major barriers to post discharge engagement identified through the ReCharge 1 formative research and based on reflective discussion and engagement with local expertise.

The package will be overseen by a physician working at the discharging hospital and will be supported and managed by a Community Liaison Officer. This package will consist of enhanced discharge planning, made possible by a discharge card that physicians will complete. The card will capture a summary of the discharge plan and follow-up appointment schedule for the discharged patient. At the time of discharge, the CLO will get involved to inform the patient about the program and if willing to be enrolled, the patient will be recruited into the programme.

After discharge, the package for the enrolled patients will include home delivery of HIV support services to be provided a by community health worker (CHW) with support and coordination provided by the CLO based at the hospital. Additional technical support will also be provided physician based at the hospital. Once the patient has been recruited into the programme, the CHW will provide the first home visit within 7 days of hospital discharge. Several additional homes visits together with phone-based support will occur thereafter. The CHW visits will consist of the following elements:

- **Vital signs assessment:** As is currently standard with UMB CHW home visits, the CHW measures the pulse and blood pressure using an electronic cuff and enters these into their tablet. If outside of safe ranges (per WHO ranges), the table prompts immediate escort to nearest health facility
- **Symptom screen:** in addition to standard warning signs (such as the four TB screening questions), screening questions could be tailored based on discharge information (i.e. confusion following admission for crypto)
- **Medication check:** The CHW will verify (visually) that patient has filled all medications, both ART, and non-ART (for ATT, hypertension, etc.) prescribed as per the discharge summary, and perform pill counts to verify proper adherence. Patient and caregivers will be counseling on why each medication was prescribed and what are expected side effects. If prescriptions have not been filled, then CHW can assist in facilitating medication dispensation from their outpatient clinic.
- **Outpatient follow-up verification:** At the first visit (within one week), the CHW will discuss with patient and care giver the timing and location of follow-up. They will remind the client by phone 1 day before and if the patient misses that visit, the CHW will arrange to

accompany the patient to the clinic at the soonest possible time. In Zambia, the standard post-hospital follow-up at outpatient occurs at 2 weeks.

- **Identify knowledge gaps among patient and family related to the reason for illness:** The CHW will document the reason for illness and the family's and patient's understanding of the illness and list any questions they have.
- **Screening for behavioral health comorbidities:** The CHW will screen for symptoms of depression and unhealthy alcohol use at ~1 month after discharge and make referrals as feasible.
- Conduct a quick home observation to document the patient home environment to assess barriers existing as well as facilitators to engagement.

To ensure that CHWs are fully supported, they will meet with CLO once per week to discuss their clients. CLOs reinforce adherence to the model. The CHW will also call their CLO supervisor urgently from the client household if certain parameters are outside of range, such as elevated pulse. The CLO can then engage the physician as needed.

The ReCharge CHW intervention holds promise. First, it was designed based on a rigorous local formative project (ReCharge 1) and with inputs from clinical, community, and program experts and MOH. Also, CHW support is both highly feasible and acceptable, but can reduce death in PLWH. In the REMSTART trial, weekly home visits plus testing and treatment of cryptococcal disease among people with low CD4 reduced mortality significantly. Many of our clients will have CD4 >200; however, given their recent hospitalization, they are at high risk of mortality.

## 5.2 Intervention evaluation: pre/post implementation trial

### 5.2.1 Study Design

We plan to conduct a prospective pilot study among 100 PLHIV at study sites who will receive the ReCharge CHW intervention model. Although a range of outcomes will be assessed, and comparisons will be made to a historical control group, the main goal is to demonstrate feasibility and acceptability. If these are demonstrated, we will seek approval and resources for a fully-powered evaluation of the program.

### 5.2.2 Historical control data:

To make inferences around possible impact, which will inform the sample size of a fully-powered future trial, before implementation of the intervention, we will collect historical control data on the outcomes of interest. We acknowledge that our comparison of trial outcomes to those from historical controls will be prone to time trends in patient outcomes and in clinical practices, which could make the intervention appear to have spurious effects. To minimize this bias, we will collect historical control data on discharged patients just prior to implementing the intervention. These will be participants with the same inclusion/exclusion criteria as intervention patients and recruited in the same way.

### 5.2.3 HIV clinical care:

Participants will receive routine HIV clinical care per national guidelines. For example, participants with high VLs at enrollment or at 6 months will be assumed to have poor

retention/adherence and will be referred for a period of enhanced adherence counseling. If adherence improves but VL remains high, clinicians are recommended to switch the regimen. We expect our participants will be physically ill; therefore, they will likely be referred for a post-discharge appointment within 1-2 weeks of discharge and may have frequent appointments in the post-discharge period. ART dispensations will be per clinician recommendations.

#### **5.2.4 Quantitative outcomes:**

Our primary effectiveness outcome will be alive and virally suppressed at 6 months after hospital discharge. Patients who either pass away or have a viral load >60 copies/ml will be considered failures. Patients who are alive but have unknown VL will also be considered failures. Those who transfer care outside of Lusaka District (we expect this to be 2-3%, based on a prior study) will be censored. We will also evaluate numerous secondary outcomes, including retention on ART, defined as possession of ARVs within 30 days of the 6-month post-discharge time point, consistent with PEPFAR TX\_CURR definition. We will also assess ARV adherence (based on medication possession ratio), number of visits attended, and the rate of hospital re-admission.

To ascertain these outcomes, our research assistant will contact the client each month post-discharge to check vital status (alive versus dead) and whereabouts. At 6 months after discharge, we will confirm the location of last HIV care and arrange for patient to have HIV VL, either back at the hospital or at their local clinic. The team will extract electronic medical records from the clinic including visit, pharmacy, and laboratory data, including HIV viral load results. Transfers within Lusaka (where there are 30+ ART clinics) are common and this approach will allow us to have complete end-line data for most clients, including historical controls and pilot participants.

We will also collect implementation outcome data during the trial, such as proportion of trial participants who do not receive any CHW services, the number and type (phone calls, home visits, meetings at the facility) of interactions between participants and CHWs. Semi-structured interviews with a subset of patients will be done to check acceptability of the intervention.

To begin to understand and anticipate meaningful patterns in our pilot data, we will also collect socio-demographics and socio-economic data on patients and their households, as well as capturing extent and severity of co-morbidities. We will include the following measures, captured at the following time points:

At enrollment/in hospital:

- Education (highest completed grade attained) for patient and primary caregiver
- Age, marital status, number of children
- Relationship to household head
- Religion and religiosity (affiliation, frequency of church attendance (weekly))
- Distance to referral health clinic and to referring hospital (time takes to get to clinic / mode of transit)

At one month:

- Mental health screening (PHQ)
- Alcohol screening (AUDIT)
- Household food insecurity (HFIES scale)
- Household asset-based wealth index (DHS module)

### 5.3 Qualitative study: feasibility, acceptability, and implementation factors

#### 5.3.1 Study Design

To characterize feasibility and acceptability, we prospectively enroll up to 100 hospitalized adults with HIV and provide them with the ReCharge CHW intervention. We will measure various indicators of feasibility. We will recruit and follow up longitudinally a cohort of participants (n=24) prospectively through the intervention, interviewing them at the start one or two weeks after being enrolled into the project and after the end of the intervention to understand the determinants of feasibility and acceptability. We will also include participants' primary caregivers in interviews after towards the end of the intervention (n=20). Acceptability and feasibility will also be assessed through IDIs with the CLOs (n=2-4) and CHWs (n=4-8) involved in the pilot implementation as well as up to 6 other healthcare workers that will be based at the hospital and community clinic.

The patient sub-sample will be followed longitudinally using a qualitative study variation of responsive and adaptive design approaches (see Table 2). IDIs will be conducted and transcribed by trained research assistants.

IDIs are best suited to capturing individual experience and perceptions, our main objective with these study populations. The sample size for each study population category anticipates what is required to reach saturation on key themes, but may be supplemented if necessary, particularly likely for patients and caretakers. Data collection tools will be informed by Andersen's Behavioral Model of Health Services Use which emphasizes the multi-level influences on health seeking behavior and related outcomes including enabling resources (e.g. family support, transportation), predisposing characteristics (e.g., self-stigma, knowledge), as well as broader healthcare system and external environmental influences.

**Table 2: Sample & methods: qualitative study of CHW pilot**

	Enrollment	1-3 months	Endline	Total
Patients IDIs	24		20-24	16*
Caregiver IDIs			12 to 16	16-20
CLOs/CHWs IDIs		6	6	6
Hospital/ Facility- HCWs			6-10 IDIs	6-10

*\*Reflects total number of patients followed longitudinally*

### 5.3.2 Qualitative participants criteria and recruitment

**Patients and caregivers:** We will begin with an oversample of 24 patients (every 3rd enrollee will be selected, adjusted to ensure a sex-stratified sample) to capture a total of 16 patients and their caregivers, stratified by retention in care, by endline (8 with high retention, 8 with low retention). IDIs at enrollment will establish a relationship, gather key insights toward understanding what led to the patient's hospitalization, gather expectations of post-discharge health, care, and anticipated barriers and enablers to retention in HIV care. As we identified in the formative phase of this work, many of the challenges patients face after discharge stem from concerns that resulted in their hospitalization (e.g., internalized stigma, concerns with disclosure and acceptance of their status, co-morbidities that require complex management in the context of limited household resources). The CHWs assigned to the patient will introduce the patient to a member of the qualitative research team either during hospitalization, or at the first home visit. The participant will then decide if they would be willing to talk with the interviewer either while being admitted or 1 week after discharge. If the patient is too sick or feels more comfortable to be interviewed after discharge, these interviews will take place within a week following the first CHW home-based visit at a time and place convenient for the discharged patient.

At the six-month follow-up, we will re-interview up to 16 of these 24 for a second IDI reflecting on patient experience and capturing their perceptions of whether and how CHW follow-up addressed barriers or enhanced enablers to care to assess feasibility and acceptability. We will work with CLOs, CHWs, and clinic-level data to stratify the endline sample by patient outcome (retained versus not retained), and purposively select patients within strata to capture a range of demographic and facility-level characteristics. The same interviewer who interviewed the patient at time 1 will return to complete the interview at time 2. Again these interviews would take place at a time and place convenient for the patient. The interviewer will then ask the patient for permission to invite their primary caregiver to be interviewed as well. If the patient and the caregiver consent, then the interviewer will also interview the care giver. Caregiver IDIs will address the experience of caring for the discharged patient throughout the intervention and their perceptions of CHW follow-up. When non-retained participant deaths are ascertained, we will try to perform an IDI with the caregiver (after reasonable time elapses for mourning) to understand the barriers to care, co-morbidities and other mortality causes (we estimate up to 4 such cases based on COLAH); we may therefore have more caregiver than patient endline interviews.

In addition to the longitudinal sub-sample of 16 patients stratified by re-engagement in care outcomes; we will also purposively sample up to 8 patients (for a total of up to 24 endline interviews) who showed signs of mental illness or behavioral health concerns (i.e., scored above  $\geq 10$  points on the PHQ-9 screening tool for depression and related concerns; or scored above  $\geq 3$  on the AUDIT-C), and were referred by the team for mental health services. We will interview these patients to understand experiences of patients with mental health related challenges such as depression and alcohol abuse, and to assess how the referral process and related services were received by such patients. These interviews will be essential toward preparing for future work with patients experiencing similar challenges.

CHWs: We will conduct two repeat IDIs with 2-4 CLOs and 4-8 CHWs (midline and endline), to understand their experience with program delivery both during and at the end of the intervention. The IDIs will focus on individual experiences with specific patients (positive and negative) and can be used to triangulate patient perceptions and programmatic challenges.

Facility-based HCWs: To understand coordination and care continuity from hospital discharge, to community, to an outpatient facility, we will conduct IDIs with 6 HCWs (2 hospital based, 4 clinic based) on their experience with CHWs and discharged patients. These will include inpatient staff, where we will address perceived advantages and disadvantages of CHW follow-up for quality of inpatient and outpatient care following discharge.

## 6. Study population

### 6.1 Description of the study site

This study will be conducted at tertiary care hospitals in Lusaka. Lusaka has a high prevalence (~18%) of HIV infection among adults. Lusaka has 36 primary public-sector health centers (25 of which are currently supported by CIRKUITS), six Level 1, and two Level 3 Hospitals, one of which is UTH. UTH outpatient departments, because of their unique capacities in Zambia, provide care for people from all provinces. However, >85% of admitted patients are from Lusaka.

The UTH Department of Medicine is the largest of departments, with 280 inpatient beds and 10,000-12,000 admissions per year (20-30 per day), 50-70% of whom are HIV-positive. Within DOM, a robust counselor-led (lay health worker) opt-out HIV rapid testing program is in place. This program reaches >90% of new admissions; the remaining 5-10% are not tested due to severity of illness. The median length of hospital stay is ~7 days. Patients stay in one of four open wards, each with 60-80 beds, and one clinician team (consisting of a Consultant, one senior, and 3-4 junior house officers) is in charge of each ward. Laboratory tests are provided by the UTH central laboratory.

Levy Mwanwasa University Teaching Hospital (LMUTH) was recently upgraded to a level 3 facility, overseen by Lusaka Provincial Health Department. Within just several years its ART department has grown >1,000 patients. The inpatient Department of Medicine includes >100 beds and 40-60% are with HIV. Inpatient and discharge procedures are very similar to UTH and the LMUTH laboratory offers similar testing capacity.

### 6.2 Description of the study population

This study will be conducted among all adult patients living with HIV who are admitted to 'E Block' medical wards at the University Teaching Hospital and Internal Medicine wards at LMUTH in Lusaka, Zambia between 1 January 2023 and 1 June 2024.

### 6.3 Participant inclusion and exclusion criteria

- Hospitalized patients living with HIV soon to be discharged (n=100)
  - Inclusion criteria: (i) age 18+ years, (ii) HIV-positive, (iii) hospitalized for at least 1 night at study site, (iv) clinically stable and expected to be discharged according to their clinician, and (v) objective evidence of suboptimal HIV outcome, defined as HIV VL above the lower limit of the assay or CD4 count <=200.
  - Exclusion criteria: (i) unable to provide informed consent, (ii) no phone, (iii) planning to reside outside of Lusaka urban district after discharge
- Health systems leaders for one-on-one key informant interviews (around n=6):
  - Inclusion criteria: (i) age 18+ years old, (ii) experienced administrators and clinical heads in Zambia, and (iii) professional experience at UTH or another health facility in Lusaka
  - Exclusion criteria: (i) declines to participate.
- CHWs providing ReCharge intervention, for interviews (n=4-8):

- Inclusion criteria: (i) age 18+ years old, (ii) HIV peer educator or psychosocial counselor, and (iii) at least 2 years of experience supporting HIV care uptake at the community-level
- Exclusion criteria: (i) declines to participate.
- Caretakers of patients living with HIV who received the ReCharge intervention (up to 20)
  - Inclusion Criteria: (i) age 18+ years old, (ii) serves as primary caretaker for participant-patient, (iii) resides with patient the majority of the time
  - Exclusion criteria: (i) patient does not permit inviting caretaker to participate, (ii) declines to participate

## 6.4 Participant recruitment

### 1. Hospitalized patients living with HIV being discharged home

Our team will integrate with the inpatient teams at the Internal medicine units at study sites. We will solicit from the teams patients who may be eligible to enroll. A research team member will assess criteria and if eligible the patient will need to provide written informed consent to enroll. We expect that 30-40% of adults admitted to Internal medicine have HIV, and among them, about 30% will meet criteria to participate. We expect it will take 3-4 months to enroll the needed sample size.

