## **8. Statistical Considerations**

### **8.1 Sampling frame and Sample Size Calculations**

#### ***8.1.1 Quantitative sample Size***

Our sample size calculation was based on the hypothesis that CHW follow-up will have substantial impact on the proportion who are alive and fully HIV virally suppressed at 6 months. To detect a change in retention from 60% (based on prior studies) to 80% between historical controls and pilot study participants, with a two-sided alpha and 80% power, we would need a sample size of at least 82 pilot participants. We expect that, because of the clinical acuity of participants, some may pass away before discharge occurs, and these would be censored and not included in main analysis. Hence, we will inflate the sample to 100.

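### The plan promises that historical controls are recruited in the same way as pilot patients but gives no procedure that secures it, so a difference in selection between periods could pass for an effect

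*Combined protocol and SAP*

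**What the plan says.** On historical controls, Section 5.2.2 states: "These will be participants with the same inclusion/exclusion criteria as intervention patients and recruited in the same way". The only bias it names is time trends in outcomes and clinical practice.

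Section 6.4 (item 1) gives the recruitment route for hospitalized patients and does not separate controls from pilot patients: "We will solicit from the teams patients who may be eligible to enroll". A research team member then checks the criteria, and the patient gives written consent. Criterion (iv) in Section 6.3 depends on the treating clinician's judgement that the patient is stable and about to go home.

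Section 5.1 describes a further step at discharge for the intervention: "the CLO will get involved to inform the patient about the program and if willing to be enrolled, the patient will be recruited". The sentence goes on to say that this recruitment is into the programme. The CLO supports and manages the package. No such step is described for controls.

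No section gives a consecutive-approach rule, a screening log or a record of refusals for either period. Section 8.2.1 plans multivariable adjustment for potential confounders without naming them, and concedes that the study is under-powered for it.

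**The concern.** A pre/post comparison with historical controls is only as good as the likeness of the two groups. Three features leave that likeness unprotected: clinicians choose whom to put forward, far more patients are eligible than are needed, and pilot patients pass a filter on willingness that controls are not described as passing.

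A difference between periods is easy to imagine. Controls agree to follow-up, while pilot patients also accept home visits. In the pilot period hospital physicians also complete the discharge card that belongs to the package (Section 5.1), so those asked to suggest patients may see the task differently. Section 2.2 names non-disclosure and weak family support as reasons for poor outcomes after discharge. Patients with those problems might decline home visits more often, which would leave a pilot group with better prognosis. Disclosure is not among the enrolment measures listed in Section 5.2.4, so adjustment might not reach it. Conversely, clinicians might steer their sickest patients toward extra support, which would hide a benefit.

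The comparison serves a secondary objective (Section 4.2), but Section 8.1.1 builds the sample size on it, Section 5.2.2 uses it to size a future trial, and Section 8.2.1 expects its estimates to support future use of the intervention.

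**Working it through.** **1. The plan's own figure.** Section 8.1.1 gives its target as follows: "To detect a change in retention from 60% (based on prior studies) to 80% between historical controls and pilot study participants". The test is two-sided, power is set at 80%, and the stated minimum is 82 in the pilot group. The alpha level and the number of controls are not stated; I assume 0.05 and equal groups. With pooled variance and no continuity correction:

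n = [z(0.975)·√(2·p̄·(1−p̄)) + z(0.80)·√(p1(1−p1) + p2(1−p2))]² / (p2−p1)²

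With p1 = 0.60, p2 = 0.80, p̄ = 0.70: [1.960·√0.42 + 0.8416·√0.40]² / 0.04 = (1.2702 + 0.5323)² / 0.04 = 81.2, rounded up to 82 per group. The figure reproduces, and it implies a control group as large as the pilot group. The plan then says: "Hence, we will inflate the sample to 100".

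**2. Room for selection.** Inputs: 10,000-12,000 UTH medical admissions a year (Section 6.1); 30-40% with HIV, about 30% of those eligible, and 3-4 months to enrol (Section 6.4).

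- Eligible per month: 10,000/12 × 0.30 × 0.30 = 75, up to 12,000/12 × 0.40 × 0.30 = 120.
- Over 3-4 months: 225 to 480. Share needed for 100: 100/480 = 21% to 100/225 = 44%.
- With the 50-70% HIV share of Section 6.1 instead: 125-210 a month, 375-840 in all, so 100/840 = 12% to 100/375 = 27%.

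The second hospital, LMUTH, would add to the pool.

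**3. Spurious difference (assumed inputs).** The documents give no success rates by type of patient. Suppose that easier-to-engage patients succeed 70% of the time and others 50%, and that the programme has no effect.

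- Spurious difference = (0.70 − 0.50) × shift in mix.
- A shift of 10 points gives 2 points; a shift of 30 gives 6.
- Ceiling: a 60% control rate means a half-and-half mix, since 0.5 × 0.70 + 0.5 × 0.50 = 0.60. If every pilot patient were easier to engage, the pilot rate would be 70%, a difference of 10 points. The same arithmetic gives at most −10 points in the other direction.

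**4. Effect on the test.** With no true effect and spurious difference d, the chance of a significant result in favour is Φ[(d − 1.960·se0)/se1]. Here se0 is the pooled standard error and se1 the unpooled one. For d = 0.06 and 82 per group: se0 = √(0.63 × 0.37 × 2/82) = 0.0754; se1 = √((0.24 + 0.2244)/82) = 0.0753; (0.06 − 0.1478)/0.0753 = −1.17; probability 12.2%.

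| Spurious difference | 82 per group | 100 per group |
|---|---|---|
| 0 | 2.5% | 2.5% |
| 2 points | 4.5% | 4.7% |
| 6 points | 12.2% | 13.9% |
| 10 points (ceiling) | 26.7% | 31.6% |

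**5. Carry-over to the next trial.** By the formula in step 1, 60% versus 75% needs 152 per group and 60% versus 70% needs 356. A true 15-point gain inflated by 5 points (0.20 × a 25-point shift) would look like 20 and suggest 82 per group, where power is 53.7%. At the ceiling, a true 10-point gain would look like 20, and power at 82 per group would be 26.7%.

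**The case against.** A reader might infer that controls are in fact recruited differently. The documents do not support that. Section 5.2.2 says the opposite. Section 6.4 can be read as one route for both groups, with research staff obtaining study consent and the CLO step following as entry to the programme; the wording in Section 5.1 about recruitment into the programme fits that reading. Nomination by ward teams does not bias the comparison if it works alike in both periods, and no section shows that it changes. The direction is unknown. The requirement of a detectable viral load or a CD4 count of 200 or below applies to both groups and limits steering toward well-controlled patients.

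The figures have limits too. A surplus of eligible patients shows room for selection, not differential selection. The 12% end pairs the HIV share in Section 6.1 with an eligibility rate that Section 6.4 gives beside a lower share. The admissions count may include repeat stays and wards outside the E Block wards named in Section 6.2, and refusals are not allowed for. The success rates and mix shifts in step 3 are assumptions. Finally, Section 5.2.1 makes feasibility and acceptability the main goal.

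All of this stands and sets the strength of the point. It leaves three gaps: the promise of equal recruitment has no procedure behind it, Sections 5.1, 5.2.2 and 6.4 are not reconciled, and without a log nobody could check afterwards whether the groups were comparable.

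**Conclusion.** The point holds as an unsecured promise, not as a demonstrated difference in recruitment. Most eligible patients will not be enrolled, no rule decides which ones are, and the pilot pathway has a willingness step without a described counterpart for controls. If nomination or willingness differs between periods, the pre/post difference will carry that selection in either direction. Under the 70%/50% assumption, a mix shift of 10-30 points gives 2-6 points, and the chance of a falsely significant result in favour rises from 2.5% to 4.5-12.2% at 82 per group. Ten points is an extreme under those rates, not a likely value. A reader might also infer that the pilot as a whole is undermined. It is not, because the feasibility and acceptability aims do not depend on the controls. What is exposed is the effect estimate on which the sample size rests and which is meant to inform the later trial. The change is worth making because it is cheap.

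**What to change.** Reconcile Sections 5.1, 5.2.2 and 6.4, and write one recruitment procedure for both periods:

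- The research team member who already assesses eligibility approaches eligible patients expected to be discharged in one fixed consecutive order at each site, in place of ward-team nomination. The plan should name the source list for each site. At UTH, where "a robust counselor-led (lay health worker) opt-out HIV rapid testing program is in place", the testing records could serve as a cross-check; Section 6.1 does not explicitly describe the same programme at LMUTH.
- Study consent is obtained before the CLO offers the programme.
- The comparison includes everyone who consents and is discharged, whether or not they take up the programme, and keeps the plan's exclusion of transfers.
- One log of eligible, approached, consented and refused patients is kept in both periods and reported beside the comparison.

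The cost is a short log and a little extra screening time each day. Clinician judgement remains through criterion (iv) in Section 6.3. If the pilot-period consent itself has to describe home visits, willingness may still differ between periods; the refusal counts would then let a reader judge how far.
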